Official Title of the study:

Serum Uric Acid Levels and Initial Presentation of Cardiovascular Diseases: a CALIBER Study

NCT number:

Not yet assigned

Date of the document:

23 January 2018

Serum Uric Acid and the Incidence of 13 Cardiovascular Diseases

[name], 23 January 2018

INTRODUCTION

Serum uric acid (SUA) is the final metabolic product of purine, which is generated in the liver and intestine by xanthine oxidase and is excreted from the urine [1]. SUA level has been observed to be associated with the risk of developing cardiovascular diseases (CVDs) in some studies [2-4], while other studies showed controversial results [5-7]. Although currently remains unclear, several pathologic mechanisms have been promoted to explain the effect of SUA on CVDs, including deleterious effects on endothelial function, oxidative metabolism, platelet adhesiveness, hemorheology, and aggregation [8-14].

An umbrella review published in June 2017 on BMJ [7] summarized evidence from clinical studies investigating the relationship between SUA levels and CVDs. None of them estimated the lifetime incidence associated with SUA attributable to the initial presentation of specific CVDs. Although one previous study investigated the association between SUA and the initial presentations of coronary heart disease, the outcome was composite [5]. Besides, previous studies have not estimated the association between SUA and eight endpoints, namely stable angina, unstable angina, subarachnoid haemorrhage, intracerebral haemorrhage, peripheral arterial disease, abdominal aortic aneurysm, and cardiac arrest/sudden cardiac death, and total cardiovascular disease.

We will address these gaps in one large prospective British cohort. Our objectives are to estimate the association between SUA and future risk of 13 of the most common initial cardiovascular presentations.

METHODS

Study overview

We will first conduct an observational study in the CALIBER (Clinical disease research using LInked Bespoke studies and Electronic health Records) programme cohort [15] to estimate the association between SUA and the incidences of the initial presentation of 13 CVDs.

Study population

We will select anonymised patients from the CALIBER cohort [15], which links four sources of electronic health data in England: the Clinical Practice Research Datalink (CPRD) with primary healthcare records, the Hospital Episode Statistics (HES) with hospital discharge information, and the Office for National Statistics (ONS) mortality and social deprivation data.

A patient will be included if he or she: a) was registered between January 1, 1998, and September 2015; b) aged 30 years or older at study entry; c) had no record of

previous diagnosis of cardiovascular disease; d) had been followed up for at least one year before the study entry; e) had at least one uric acid measurement.

Exposure

The main exposure will be the baseline serum uric acid (SUA) level measured within one year of the study entry as recorded in primary care. If a patient had more than one measurement, the mean of the values will be taken. We will perform sensitivity analyses to use the SUA level recorded closest to the study entry.

Since gout is an important complication of hyperuricaemia and is associated with CVDs, we will also classify the patient state at baseline as with gout or with no gout, regardless of SUA levels, based on the diagnosis within one year of the study entry. Participants who developed new-onset gout during follow-up will be analysed according to their baseline status of no gout.

Covariates

The following baseline covariates will be considered:

- a) Sociodemographic: sex, age and index of multiple deprivation;
- b) Cardiovascular risk factors: body mass index, systolic blood pressure, high-density lipoprotein (HDL) cholesterol, low-density lipoprotein (LDL) cholesterol, triglyceride, and estimated glomerular filtration rate, smoking status, alcohol consumption;
- c) Medication use: any prescription in the year before index date of blood pressure lowering drugs (including diuretics, beta blockers, ACEIs, ARBs), statins, non-steroidal anti-inflammatory drugs (NSAIDs), aspirin, immunosuppressant drug, and in women only, oestrogen oral contraceptives and hormone replacement therapy;
- d) Comorbidities (defined by Read codes, a coded thesaurus of clinical terms used in the UK, in primary care data and by ICD-10 codes in hospital care data): Cancer, diabetes, asthma or atopy, COPD, connective tissue disease, inflammatory bowel diseases.

For continuous variables (BMI, systolic blood pressure, and cholesterol), we will use the most recent value in the year before the study entry. For alcohol consumption, we will use the most recent record in the five years before entry to classify participants' drinking behaviour into five categories: non-drinkers (Read codes as "teetotaller" or "non-drinker"), former drinkers (Read codes as "stopped drinking alcohol" or "ex-drinker"), occasional drinkers (Read codes as "drinks rarely" or "drinks occasionally"), current moderate drinkers (Read codes as "alcohol intake within recommended sensible limits" or "light drinker"), and heavy drinkers (Read codes as "alcohol intake above recommended sensible drinking limits" or "hazardous alcohol use").

We will impute missing covariate values using multiple imputation, as implemented in the “mice” algorithm in the statistical package R. We will extract the following values of the continuous variables to use as auxiliary variables for multiple imputation: the first measurement after the time window and the most recent measurement before the time window, along with the timing of these measurements relative to the study entry. We will check whether the imputations are plausible by comparing plots of the distribution of recorded and imputed values of all variables.

Follow up

The observation period for all participants will begin on the date when all the study inclusion criteria are fulfilled. Participants will be followed up until the occurrence of an initial presentation of cardiovascular disease, death, or de-registration from the practice, whichever occurred first.

Endpoints

Endpoints will be the initial presentation of cardiovascular disease as any of the following 13 CVDs diagnosed in primary care (defined by Read codes), secondary care (defined by ICD-10 codes), or at death.(defined by ICD-10 codes): Stable angina, unstable angina, myocardial infarction, unheralded coronary heart disease death, heart failure, cardiac arrest/sudden cardiac death, transient ischaemic attack, ischaemic stroke, subarachnoid haemorrhage, intracerebral haemorrhage, peripheral arterial disease, abdominal aortic aneurysm, atrial fibrillation, and a composite total cardiovascular disease (all 13 cardiovascular diseases combined). An example is given by the definition of atrial fibrillation [16]

Statistical analysis

We will analyse the SUA level as a categorical variable in order to avoid presuming a particular shape for the association with CVDs. Since the normal range for SUA and the diagnosis cut-off for hyperuricemia diagnosis varies [17-19], we will use the following cut-offs:

- 1) 3 mg/dL (180 umol/L, the lower limit of target SUA level for long-term management recommended by the 2016 updated EULAR guideline [20]),
- 2) 4 mg/dL (240 umol/L),
- 3) 5 mg/dL (300 umol/L, the target SUA for severe cases or patients with tophi recommended by various guidelines [20-23]),
- 4) 6 mg/dL (360 umol/L, the general target SUA for long-term management recommended by various guidelines [20-23]),
- 5) 7 mg/dL (420 umol/L).

If the shape of the association between SUA and CVDs is found to be linear, we will then perform analyses with SUA level as a continuous variable.

Quantitative variables will be summarized in mean and standard deviation and qualitative variables in number and percentages. Between group differences of

parametric values will be compared using analysis of variance (ANOVA) and that of categorical variables using chi-square tests.

We will plot crude cumulative incidence curves for each specific cardiovascular endpoint for people with SUA levels between 240-300 umol vs. 360-420 umol/L, using age as the timescale, under a competing risks framework (i.e., participants could experience only one initial presentation).

We will use multivariable Cox regression to calculate cause-specific hazards for associations between categories of SUA levels and initial presentations of cardiovascular disease. We will plot Schoenfeld residuals to verify the proportional hazards assumption.

In the primary analysis, we will adjust for age (linear and quadratic), sex, index of multiple deprivation, diabetes, smoking status, BMI, systolic blood pressure, HDL cholesterol, LDL cholesterol, and prescription of statins or antihypertensive medication in the year before study entry. The baseline hazard function of each model will be stratified by general practice and sex, and we will use multiple imputation to account for missing covariate data.

Assuming independence in effects, heterogeneity in associations across CVD endpoints for the fourth vs. the first quintile will be assessed with tau-square statistic, which is the between-CVD endpoint variance, and I^2 that can be interpreted as the proportion of the total variation in estimates that is due to heterogeneity.

We will conduct a series of sensitivity analyses:

- a) Covariate adjustment: We will conduct analyses adjusted for age and sex only, and analyses adjusted for age, sex, and cardiovascular risk factors. We will assess interactions with age and sex.
- b) Gout: We will categorise patients into with gout and with no gout, regardless of SUA.
- c) Imputed data: We will check whether the imputations are plausible by comparing plots of the distribution of recorded and imputed values of all variables.
- d) Data source: We will conduct analysis ignoring endpoints recorded only in primary care (CPRD).
- e) Endpoints: We will conduct analysis restricting endpoints to fatal endpoints.
- f) Time: We will conduct analysis restricting participants to individuals who entered the study after 2004 (when recording of covariates would be expected to be more complete after introduction of the Quality and Outcomes Framework to incentivise good performance in the care of specified diseases).

We will conduct all analyses using R 3.4.1.

Role of funding

The funders had no role in the study design, data collection, data analysis, data interpretation, or writing of the report.

References

[5] Kavousi, M. et al. Evaluation of newer risk markers for coronary heart disease risk classification a cohort study. *Ann Intern Med*. 156, 438–444 (2012).

[6] Storhaug, H. et al. Uric acid is a risk factor for ischemic stroke and all-cause mortality in the general population a gender specific analysis from The Tromso Study. *BMC Cardiovasc Disord*. 13, 115 (2013).

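### Baseline gout counts only a diagnosis within one year of study entry, so patients whose only gout code is older join the no-gout comparator of sensitivity analysis b) and may dilute its hazard ratio

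*Protocol*

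**What the plan says.** Methods, Exposure, sets the baseline gout state as "with gout or with no gout, regardless of SUA levels, based on the diagnosis within one year of the study entry". The reason given is "Since gout is an important complication of hyperuricaemia and is associated with CVDs"; it is not limited to recently coded gout. The same section says what happens to gout that arises after entry: "Participants who developed new-onset gout during follow-up will be analysed according to their baseline status of no gout". There is no matching sentence for gout coded before the one-year window.

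The variable is used in item b) of the sensitivity analyses: "Gout: We will categorise patients into with gout and with no gout, regardless of SUA". That item gives no other definition, third category or exclusion.

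Two entry criteria under Study population bear on what can be seen in the record. Criteria c) and d) exclude a "previous diagnosis of cardiovascular disease; d) had been followed up for at least one year before the study entry". The first has no stated time limit; the second guarantees one year of prior record and sets no maximum.

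**The concern.** Gout can be on a patient's record without being coded again in the year before entry. Under a two-state rule such a patient has nowhere to go but the no-gout group, which is the natural reference for item b). The protocol's own reason for the analysis is that gout is related to cardiovascular disease, so known gout patients are an awkward part of that reference group.

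If older gout raises cardiovascular hazard, the reference hazard is too high and the estimated gout HR is pulled towards 1. If it does not, the rule is unbiased for recent gout. The documents do not say which holds, and a two-group analysis cannot show it. At stake is how a weak or null gout result in item b) should be read.

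**Working it through.** **Reading the rule.** Two states, defined by a diagnosis in a one-year window, leave no remainder. A patient with an older code and a repeat code inside the window still counts as gout; only those whose sole codes are older are affected. The wording does not say whether the year lies before or after entry, but the sentence on new-onset gout points to before.

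**Inputs.** The protocol states no gout prevalence, coding share or HR, so there is no figure to reproduce and all of these are assumptions:

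- g, gout prevalence at entry: 5–20%
- c, share of gout cases coded in the window: 20–60%
- HR of recent gout against never-gout: 1.5
- h, HR of older-only gout against never-gout: 1.5, 1.25 or 1.0

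The model has no covariates and uses a rare-event approximation.

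**Step 1: share of the comparator with older gout.** m = (1−c)g / [(1−g) + (1−c)g].

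- Lowest (g = 0.05, c = 0.6): 0.02 / 0.97 = 2.06%
- Highest (g = 0.20, c = 0.2): 0.16 / 0.96 = 16.67%

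**Step 2: HR as the rule would report it.** HR = 1.5 / [1 + m(h−1)].

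| h | m = 2.06% | m = 16.67% | log HR lost |
|---|---|---|---|
| 1.5 | 1.5/1.0103 = 1.48 | 1.5/1.0833 = 1.38 | 2.5% to 19.7% |
| 1.25 | 1.5/1.0052 = 1.49 | 1.5/1.0417 = 1.44 | 1.3% to 10.1% |
| 1.0 | 1.50 | 1.50 | none |

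A narrower assumption for m, 1–10%, gives 1.49 to 1.43 at h = 1.5.

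**Step 3: would ever-gout against never-gout do instead?** Its HR is 1.5c + h(1−c). At h = 1.25 this is 1.30 (c = 0.2) to 1.40 (c = 0.6); at h = 1.0 it is 1.10 to 1.30. Ever-gout alone can therefore understate recent gout by more than the current rule does.

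**Step 4: three groups.** Recent gout against no gout code on or before entry returns 1.50 only if every older code is visible. Take the worst case (g = 0.20, c = 0.2, h = 1.5) and suppose half of older gout is unseen. Residual contamination is 0.08 / (0.80 + 0.08) = 9.1%, and the HR is 1.5 / 1.045 = 1.43. That improves on 1.38 but does not reach 1.50.

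**Step 5: cost in precision.** The ratio of standard errors, three-group to current, is sqrt{[1/(cg) + 1/(1−g)] / [1/(cg) + 1/(1−cg)]}. At g = 0.20, c = 0.6 it is sqrt{(8.333 + 1.250) / (8.333 + 1.136)} = sqrt(1.0120) = 1.006, the largest value in the range. Replacing group sizes by expected events at h = 1.5 gives sqrt{(5.556 + 1.250) / (5.556 + 1.087)} = 1.012.

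**The case against.** The strongest reply is that this is a design choice. The one-year window matches those for uric acid and prescriptions, and one year is the only history that criterion d) guarantees, so every patient has the same minimum look-back. For recent gout against everyone else, the rule estimates what it defines; dilution exists only relative to a never-gout comparator. Item b) also names no model or HR, so the affected estimate is inferred from gout's place under Exposure.

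Much of this stands. A one-year definition of the gout group is legitimate, and the point does not dispute it. What remains is the comparator: it is labelled as having no gout, and the stated rationale covers gout in general. Nor is this a detail left to an analysis plan, since the protocol itself fixes the window and the two states.

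A reader might infer more than the documents support:

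- *That the main results are biased.* The objective is uric acid: "Our objectives are to estimate the association between SUA and future risk of 13 of the most common initial cardiovascular presentations". The primary adjustment list, which begins "In the primary analysis, we will adjust for age (linear and quadratic), sex, index of multiple deprivation, diabetes, smoking status, BMI", contains no gout term.
- *That prevalence must be well above 20%, because each patient "had at least one uric acid measurement".* The documents give no figure from which to derive that, so larger dilution is not claimed.
- *That patients with older gout are lost.* They stay in the analysis, in the comparator. The smaller exposed group follows from the one-year definition, which is accepted here.

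**Conclusion.** The point holds as a minor weakness in one sensitivity analysis. On the protocol's wording, patients whose only gout code is older than a year are counted as having no gout, and nothing elsewhere corrects this. The bias is towards 1 if older gout carries excess hazard and nil if it does not. Under the assumed inputs, an HR of 1.5 would appear as 1.38 at worst and 1.50 at best: the direction of the finding survives and its size is somewhat understated. Prevalence, coding share and both HRs are assumptions, so these figures show scale and are not predictions.

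**What to change.** In Exposure and in item b), use the existing gout codes to class patients at entry as:

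1. gout coded in the year before entry;
2. gout coded only earlier;
3. no gout code on or before entry, as the comparator.

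Report this beside the one-year definition, not in place of it. The split also gives a separate estimate for older gout, which shows whether dilution was a real issue.

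The cost is about one sentence and one or two model runs on data already held. Criterion c) already calls for a search for earlier cardiovascular diagnoses with no stated time limit, so a similar search for gout is not a new kind of task. The loss of precision for recent gout is the 0.6% (1.2% weighting by events) shown above.

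The limitation is that older gout can be removed only where the record reaches back far enough. For a patient with exactly one year of history the new rule is the same as the current one. The one-year result cannot check this, because its comparator contains all older gout, seen and unseen. Repeating the three-group analysis in patients with longer prior records would be the check.

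### A continuous uric acid analysis is run only if the association proves linear, so a non-linear association is described by six bands alone and the gradient within bands, chiefly above 420 umol/L, is lost

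*Protocol*

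**What the plan says.** The protocol's Statistical analysis section opens: "We will analyse the SUA level as a categorical variable in order to avoid presuming a particular shape for the association with CVDs". It lists five cut-offs, 180, 240, 300, 360 and 420 umol/L (3 to 7 mg/dL in steps of 1). Some are tied to treatment targets in gout guidelines, for example "6 mg/dL (360 umol/L, the general target SUA for long-term management recommended by various guidelines". The next step is conditional: "If the shape of the association between SUA and CVDs is found to be linear, we will then perform analyses". Those further analyses would enter SUA as a continuous term.

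The cause-specific Cox models use the SUA categories for every initial presentation. The crude cumulative incidence curves compare only the 240-300 and 360-420 bands, so the band above 420 is not plotted. Neither the main analysis nor the list of sensitivity analyses contains a spline, polynomial or other flexible continuous term for SUA.

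**The concern.** The stated aim is not to presume a shape. Bands presume less than a straight line does, and they can show a J or a U. They still fix the hazard as constant within each band, with a jump at each cut-off. That matters most in the open top band, where everyone above 420 umol/L shares one HR.

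The condition also works against the aim. When the association is linear, the continuous model is added, although the bands would already have shown that pattern. When it is J-shaped, or flat and then rising, no continuous model is fitted, although detail is then most useful. The choice is made after seeing the same data.

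The text leaves open whether linearity is judged once or for each endpoint. If for each endpoint, one with few events could pass as linear simply because departures from linearity cannot be detected.

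**Working it through.** **What can be checked directly.** Five cut-offs make six bands. At 60 umol/L per mg/dL, 3, 4, 5, 6 and 7 mg/dL give 180, 240, 300, 360 and 420, as listed. The protocol states no sample size, event count or SUA distribution, so there is no figure of its own to reproduce. What follows is illustration on assumed inputs.

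**Assumed inputs.** SUA is normal with mean/SD 300/80, 330/85 or 360/90 umol/L, which puts 6.7%, 14.5% and 25.3% of people above 420. Two true shapes for the hazard at SUA value x:

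- (a) flat to 420, then HR = 1.3^((x - 420)/60);
- (b) J-shaped with its lowest point at 300: log HR = ln(1.1) × ((x - 300)/60)² / 2.

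The reference is the average hazard in the 240-300 band.

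**One HR for the top band against the HR at given values.** The band HR is the average hazard above 420 divided by the average in the reference band. Point values under (a) are, for example, 1.3^(10/60) = 1.04 at 430 and 1.3^(120/60) = 1.69 at 540.

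| Shape | HR reported for >420 band | HR at 430 | at 480 | at 540 | at 600 |
|---|---|---|---|---|---|
| (a) | 1.18 to 1.29 | 1.04 | 1.30 | 1.69 | 2.20 |
| (b) | 1.39 to 1.56 | 1.23 | about 1.5 | about 2.1 | about 3.2 |

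The column for 600 is an extreme: under these distributions fewer than 0.4% of people lie above it. The 95th percentile within the top band is 517 to 561 umol/L, so 540 is the more representative upper value.

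**How a finding of linearity would depend on events.** Suppose linearity were judged by a test of departure from a straight line through the six band log HRs. It has 6 - 2 = 4 degrees of freedom and is taken at the 5% level (assumed; the protocol names no test). The noncentrality is E × Σ e_k r_k², where E is the number of events, e_k the share of events in band k, and r_k the residual of the band's log HR from the event-weighted line. The sum is 0.0013, 0.0030 and 0.0050 for shape (a), and 0.0130, 0.0156 and 0.0167 for shape (b), in the order of the three distributions. For shape (a) with 300/80, 200 events give 200 × 0.0013 = 0.26 and power of 6%; 5,000 events give 6.5 and power of 51%.

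| Events | Power, shape (a) | Power, shape (b) |
|---|---|---|
| 200 | 6 to 11% | 21 to 27% |
| 1,000 | 12 to 40% | 84 to 92% |
| 5,000 | 51 to 99% | 100% |

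The approximation ignores covariates and stratification. It shows that the same true shape could be called linear for a rare endpoint and non-linear for a common one.

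**The case against.** The case for leaving the plan alone has weight. The bands are pre-specified, evenly spaced, partly tied to guideline targets and easy to read clinically. Six bands can show a J or U shape. On normal distributions from 310/80 to 350/100 they keep roughly 92 to 94% of the variance of SUA, so the average loss is modest. The missing criterion for linearity could be in a statistical analysis plan that is not at hand, so its absence alone is no defect. All of this stands.

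A reader might infer three stronger claims, none of which the protocol supports.

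- *Risk above 420 is not estimated.* It is: the banded Cox model gives an average HR for that band for every endpoint. Only the gradient inside the band is missing.
- *Endpoints are analysed differently and cannot be compared on one scale.* The banded analysis is common to all endpoints and supplies that scale; the continuous analysis is an addition. The conditional sentence speaks of a single association with CVDs and sets no decision for each endpoint.
- *The top band hides a gradient even under a steady effect.* With a constant HR of 1.1 to 1.2 per 60 umol/L, the 5th to 95th percentile range within the top band gives 1.1^((521 - 422)/60) = 1.17 to 1.2^((575 - 424)/60) = 1.58. But that is the log-linear case, in which the plan does run the continuous analysis, so these figures do not measure the loss.

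A spline has limits too. It is linear beyond its outer knots: with mean 310 and SD 80, a last knot at the 95th percentile lies at 310 + 1.645 × 80 = 442 umol/L, and everything above is one straight line on the log-hazard scale. It still estimates a slope there, which a single band HR cannot.

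What the objection does not remove is that no flexible continuous model is planned for a non-linear association, and that the results decide whether a continuous model is run.

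**Conclusion.** The point holds as a worthwhile, inexpensive improvement. The six-band analysis is valid and gives each endpoint a coarse shape, but under a non-linear association it is all there is. On the assumed shapes, one top-band HR of 1.18 to 1.29 would stand for true values from 1.04 at 430 to 1.69 at 540 umol/L, or 1.39 to 1.56 for values from 1.23 to about 2.1. These sizes rest wholly on the assumed SUA distributions and hazard shapes.

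That rare endpoints might pass as linear for want of events is a risk, conditional on judging linearity for each endpoint and on event counts the protocol does not give. It should not be read as something the plan states or as a certain outcome.

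**What to change.** In the Statistical analysis section:

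1. Delete the sentence that makes the continuous analysis conditional on linearity.
2. Keep the six-band Cox analysis as planned.
3. Add, for all 13 endpoints and the composite and whatever the apparent shape, a restricted cubic spline for SUA in the same adjusted, stratified Cox model. Set the number of knots and their percentiles in advance, and report a test of non-linearity pooled over the imputations.
4. Report an HR per 60 umol/L (1 mg/dL) only beside the spline curve.

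The cost is a change of wording and one extra model per endpoint on data already extracted. The drawbacks are that the spline is linear beyond its outer knots, and that a per-unit HR does not on its own summarise a non-linear association.

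### The primary Cox model leaves out eGFR without a reason, so its SUA hazard ratios may carry residual confounding by kidney function for endpoints that eGFR predicts

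*Protocol*

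**What the plan says.** Under Statistical analysis, the Protocol specifies the model: "We will use multivariable Cox regression to calculate cause-specific hazards for associations between categories of SUA levels and initial presentations of cardiovascular disease". It then gives a complete list of covariates for the primary analysis: "In the primary analysis, we will adjust for age (linear and quadratic), sex, index of multiple deprivation, diabetes, smoking status, BMI, systolic blood pressure", and after that "HDL cholesterol, LDL cholesterol, and prescription of statins or antihypertensive medication in the year before study entry". The baseline hazard is stratified by general practice and sex only. eGFR is in neither place.

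Three other parts of the Protocol bear on this:

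- The Introduction says that SUA "is generated in the liver and intestine by xanthine oxidase and is excreted from the urine".
- Covariates b), the list of cardiovascular risk factors, includes "triglyceride, and estimated glomerular filtration rate, smoking status, alcohol consumption". The comorbidities in Covariates d) contain no kidney disease.
- Sensitivity analysis a) plans one model with age and sex alone, and another that adds the cardiovascular risk factors. That phrase matches the label of Covariates b), so the second model probably contains eGFR.

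On baseline values, Covariates states: "For continuous variables (BMI, systolic blood pressure, and cholesterol), we will use the most recent value in the year before the study entry". eGFR is not named there. Imputation is general: "we will use multiple imputation to account for missing covariate data".

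**The concern.** By the Protocol's own account, kidney function bears on both sides of the association. SUA is cleared through the urine, and eGFR is classed as a cardiovascular risk factor. A variable linked to exposure and outcome in this way is a candidate confounder, and the primary model has no direct control for it.

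If people with lower filtration have higher SUA and a higher hazard of a given endpoint, part of the primary hazard ratio for a high SUA category reflects kidney function and not SUA. The study describes its cohort as large. Narrow confidence intervals would not reveal a systematic shift of a few per cent.

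Leaving this to a statistical analysis plan would not settle it, because the Protocol itself fixes the primary adjustment set.

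**Working it through.** The Protocol gives no sample size, event count or effect size, so there is no figure of its own to reproduce. The check has two parts.

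**1. The covariate lists side by side**

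| Covariate | Primary model | Sensitivity a), second model, if it means list b) |
|---|---|---|
| Age, sex | yes | yes |
| BMI, systolic pressure, HDL, LDL, smoking | yes | yes |
| Deprivation index | yes | not named |
| Diabetes | yes | not named |
| Statins or antihypertensives | yes | not named |
| Triglyceride | no | yes |
| Alcohol | no | yes |
| **eGFR** | **no** | **yes** |

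As worded, the two models differ in six rows, not one. A change in the SUA hazard ratio between them could not be attributed to eGFR.

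**2. Possible size, on assumed inputs**

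Treat reduced eGFR as an omitted binary confounder. Let p0 and p1 be its prevalence in the reference and comparison SUA categories, given the primary covariates, and let H be its residual hazard ratio for the endpoint. The SUA hazard ratio is then multiplied by approximately

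(1 + p1 × (H − 1)) / (1 + p0 × (H − 1)).

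Every value of p0, p1 and H here is an assumption; the document supplies none. With p0 = 0.05:

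| H | p1 = 0.10 | p1 = 0.15 | p1 = 0.25 | p1 = 0.02 (below reference) |
|---|---|---|---|---|
| 1.0 | 1.000 | 1.000 | 1.000 | 1.000 |
| 1.2 | 1.010 | 1.020 | 1.040 | 0.994 |
| 1.4 | 1.020 | 1.039 | 1.078 | 0.988 |
| 2.0 | 1.048 | 1.095 | 1.190 | 0.971 |

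For example, H = 1.4 and p1 = 0.25 give (1 + 0.25 × 0.4) / (1 + 0.05 × 0.4) = 1.10 / 1.02 = 1.078.

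The choice of p0 matters little. With p0 at 0.03, 0.05 or 0.10 and the same gaps (0.05, 0.10, 0.20), the ranges above the reference are 1.010 to 1.040 (H = 1.2), 1.019 to 1.079 (H = 1.4) and 1.045 to 1.194 (H = 2.0).

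A simulation treated eGFR as continuous, with no true SUA effect and the Protocol's cut-offs. It assumed that SUA is normal with mean 330 and SD 85 umol/L, that 240 to 300 umol/L is the reference, that SUA and eGFR correlate at −0.20 to −0.50, and that the hazard ratio is 1.1 to 1.3 per SD lower eGFR. The apparent rate ratio was:

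- 1.01 to 1.09 for 300 to 360 umol/L;
- 1.03 to 1.20 for 360 to 420 umol/L;
- 1.04 to 1.35 for 420 umol/L and above;
- 0.82 to 0.99 below the reference;
- 1.00 throughout when eGFR did not predict the endpoint.

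This simulation did not condition on the primary covariates, so it confirms direction and its sizes lean high for the adjusted model.

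**The case against.** There is a fair case for the plan as written.

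- **An eGFR-adjusted estimate is probably already planned.** Sensitivity analysis a) uses the label of the list that contains eGFR. A reader might infer that the study never adjusts for kidney function; the document does not support that. What stands is that this model is not the primary set plus eGFR, and that the primary estimate is unchanged by it.
- **There is no contradiction.** Covariates describes variables to be considered, and others on the list (aspirin, NSAIDs, cancer, COPD) also stay out of the primary model. That is right. The point concerns the choice of confounders. eGFR stands apart because the Protocol links kidney excretion to the exposure and classes eGFR as a risk factor for the outcome.
- **eGFR may be partly a mediator.** The stated aim is to estimate an association, and the title of the first cited reference raises a role for uric acid in renal disease. If SUA harms the kidney, adjusting for eGFR could remove part of its effect. This is the strongest argument, but the Protocol does not make it. It is a reason to report both models.
- **Partial control exists.** Age, diabetes and systolic pressure are adjusted for, as is antihypertensive prescription, drawn from "blood pressure lowering drugs (including diuretics, beta blockers, ACEIs, ARBs" and so on. This stands, and it makes a small residual effect more likely than a large one.
- **Direction comes from outside the text.** The Protocol says that SUA is excreted in urine. It does not say that lower eGFR raises SUA or predicts each of the 13 endpoints. The conclusion must therefore stay conditional.

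**Conclusion.** The omission is certain; its effect is conditional. For endpoints that eGFR predicts, the primary hazard ratios may carry residual confounding by kidney function, upward for SUA categories above the reference and downward below it. The Protocol names no reference category for the Cox model, so which categories fall on each side is open. Endpoints unrelated to eGFR are unaffected.

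The size cannot be derived from the document. On the assumed inputs the factor is about 1.01 to 1.19 above the reference and 0.97 to 0.99 below it. The value 1.19 needs both a residual hazard ratio of 2.0 and a 20-point prevalence gap after the existing adjustment, so the lower end is more plausible.

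A reader might infer that the primary results will be materially inflated. The document does not support that: it gives none of the inputs, and the existing covariates already absorb part of the effect. The point is worth fixing because the remedy is cheap and the variable is already on the covariate list.

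**What to change.** 1. Add baseline eGFR to the primary adjustment set.
2. State its measurement window. The one-year rule names only BMI, systolic pressure and cholesterol, so eGFR needs its own statement, for example by extending that rule to it.
3. Include eGFR in the multiple imputation with the other covariates.
4. Report the present set, without eGFR, as a named sensitivity analysis. The two models then differ in eGFR alone.

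If the investigators prefer to keep eGFR out of the primary model, the minimum is to give the reason and to specify a model with the primary set plus eGFR.

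The pair of models shows how far the SUA result depends on eGFR. It does not show why: attenuation when eGFR is added is expected under confounding and under mediation alike, so it should not be presented as a test of either.

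The cost is one covariate, one measurement rule and one named sensitivity analysis. The downsides are slightly wider intervals and possible over-adjustment if eGFR is partly a mediator.
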